## 12. EFFICACY ASSESSMENTS

### 12.1 Weekly Number of Bowel Movements

The total number of bowel movements (defecations) occurring during the second week of ECC treatment (Days 8 to 14) compared those occurring during screening in the week prior to randomization, will be used to assess the primary endpoint. Use of loperamide will also be recorded. Bowel movements will be recorded by the patients on a daily basis, as follows:

- each day of the last 14 days of the screening period, prior to randomization, to establish the first baseline and confirm subject eligibility
- each day of the first 14-day treatment period
- each day of the 14-day washout period
- each day of the second 14-day treatment period

[figure not shown]
In summary, this implies that occurrences of bowel movements will be recorded daily by the patient, in the diary, from Day -14 (screening) up to Day 42, i.e. the last dosing day of the study.

### 12.2 Bristol Stool Form Scale

The Bristol Stool Form Scale (BSFS) is a diagnostic medical tool designed to categorize and score the form of human stools into seven categories (30,31). It is used mostly in clinical research. It is sometimes also referred to as the Bristol stool chart (BSC), Bristol stool form scale, or BSF scale.

It was developed at the Bristol Royal Infirmary as a clinical assessment tool in 1997, and is widely used as a research tool to evaluate the effectiveness of treatments for various diseases of the bowel, especially Irritable Bowel Syndrome and chronic constipation. BSFS scores of 6 or 7 indicate diarrhea.

Figure 2 - Bristol Stool Chart

Reference: Lewis and Heaton (1997)

All patients will be asked to examine their stools at every bowel movement and to provide a general estimation of their form, according to the Bristol Stool Chart. This will be done at every bowel movement, every day as per the Schedule of Activities. This information will also be recorded in the patient diary.

The Mean Diarrhea Composite Index ([weekly bowel movement frequency X mean daily BSFS score] + loperamide use [weekly mg X 3]) at baseline and during the second week of treatment (i.e. Days 8-14, and Days 36-42) will also be estimated.

### 12.3 Patient Visual Analog Scale (VAS)

An 11-point Visual Analog Scale will be used to rate the patient's experience on the following 4 clinical symptoms:

- a. severity of diarrhea
- b. abdominal pain
- c. bloating
- d. urgency

The Analog Scale will look as follows:

All patients will be asked to put an X on the scale, where they grade the severity of their symptoms, as experienced over the last 24 hours. The VAS will be used by the patients on Days 0, 15, 28 and 43.

### 13. SAFETY ASSESSMENT

Safety evaluations will include reporting of Adverse Events (AEs), clinical laboratory assessments (clinical chemistry, hematology and urinalysis), ECGs, and clinical evaluation of vital signs and physical examinations performed at regular intervals during the study.

All AEs will be assessed, documented, and reported in accordance with ICH GCP guidelines.

#### 13.1 Documentation of Adverse Events

AEs will be collected from the time of informed consent signing until the last scheduled study follow-up. From screening to the first dose of the study, AEs will be recorded as screening events or as part of the medical history, as applicable. An AE is any untoward medical occurrence (which does not necessarily have a causal relationship with the treatment). An AE can be any unfavorable and unintended sign (including an abnormal laboratory finding, for example), symptom, or disease temporally associated with the use of an investigational product, whether or not related to the study drug. This includes any occurrence that was new in onset or aggravated in severity or frequency from the baseline condition. Planned hospital admissions or surgical procedures for an illness or disease that existed before the patient was screened in the study are **not** to be considered AEs unless the condition deteriorated in an unexpected manner during the study (e.g. surgery was performed earlier than planned).

Abnormal results of diagnostic procedures, including laboratory test abnormalities, are considered AEs if they result in any one of the following:

- Discontinuation of study treatment;
- Require treatment or any other therapeutic intervention;
- The necessity for further diagnostic evaluation (excluding a repetition of the same procedure to confirm the abnormality);
- Association with clinical signs or symptoms that may have a significant clinical impact, as determined by the Investigator.

Patients are encouraged to report AEs spontaneously or in response to general, non-directed questioning. All AEs are to be followed until resolution or until a stable clinical endpoint is reached. The investigator should question patients about AEs and changes in pre-existing illnesses since their last visit and must record the information in the patients' medical records. The onset and end dates, severity, relationship to study agent, action taken, and outcome must be recorded for each AE. All AEs are to be recorded on the appropriate e-CRF and in detail on the source documents.

SAEs must be reported immediately to the medical monitor, i.e. no later than 24 hours after they are known. AEs that are ongoing at the end of the study should be marked as ongoing. However, it is the responsibility of the Investigator to follow up on these events until resolution, according to standard medical care. Any SAE that the investigator becomes aware of outside of the study period should be reported to the medical monitor, for a period up to 30 days post-last investigational drug dose.

Patients who experience AEs will be monitored with relevant clinical assessments and laboratory tests, as determined by the Investigator. All AEs and laboratory abnormalities encountered during the study should be followed until resolution or stabilization of the event(s). Any action taken and follow-up results must be recorded in the patient's

medical record. Follow-up laboratory results should be filed with the patient's source documentation and e-CRF. For all AEs that require the patient to discontinue treatment, relevant clinical assessments and laboratory tests should be repeated on at least a monthly basis until final resolution or stabilization of the event(s). These assessments should be captured in the source data and SAE forms but will not be entered in the e-CRF.

All AEs for randomized patients will be recorded in the e-CRF and the patient's source documents. AEs for patients who are screened but not subsequently randomized in the study will be recorded only in the patient's source documents. The following data should be documented for each AE:

- Description of the event;
- Classification of "serious" or "not serious";
- Date of first occurrence and date of resolution (if applicable);
- Severity;
- Causal relationship to study drug(s);
- Action taken;
- Outcome;
- Concomitant medication or other treatment given.

### 13.2 Adverse Event Severity

The severity of an AE should be determined according to the definitions below. Clinically significant laboratory tests should be recorded as AEs in the patient's source documents and e-CRF.

Severity will be assessed according to the following criteria:

Classification	Definition
Mild (Grade 1)	Mild level of discomfort and does not interfere with regular activities
Moderate (Grade 2)	Moderate level of discomfort and significantly interferes with regular activities
Severe (Grade 3)	Significant level of discomfort and prevents regular activities
Life-threatening (Grade 4)	Any adverse drug experience that places the patient, in the view of the investigator, at immediate risk of death

### 13.3 Adverse Event Causality

Causality will be assessed according to the following criteria:

Classification	Definition
Definitely Related	Reasonable temporal relationship to study drug administration Follows a known response pattern (i.e., drug is known to cause this AE) There is no alternative etiology
Probably Related	Reasonable temporal relationship Follows a suspected response pattern (i.e., based on similar drugs) Little or no evidence for a more likely alternative etiology
Possibly Related	Reasonable temporal relationship Some evidence for a more likely alternative etiology
Unrelated	Does not have a temporal relationship. Or, Definitely due to alternative etiology

ICH guidelines (March, 1995) clarify “reasonable causal relationship” to mean “that there are facts [evidence] or arguments to suggest a causal relationship.”

The causality assessment must be made by the Investigator based on information available at the time that the AE/SAE worksheet is completed. The initial causality assessment may be revised as new information becomes available.

### 13.4 Study Drug Action Taken

The investigator will classify the study drug action taken with regard to the AE. The action taken should be classified according to the categories shown below:

Classification	Definition
Dose Not Changed	Study drug dose not changed in response to an AE;
Drug Withdrawn	Study drug administration permanently discontinued in response to an AE;
Not Applicable	Action taken regarding study drug administration does not apply. "Not applicable" should be used in circumstances such as when the investigational treatment had been completed before the AE began and no opportunity to decide whether to continue, or withdraw treatment is possible.

### 13.5 Adverse Event Outcome

An AE should be followed until the investigator has determined and provided the final outcome. The outcome should be classified according to the categories shown below:

Classification	Definition
Recovered/Resolved	Resolution of an AE with no residual signs or symptoms
Recovered/Resolved with Sequelae	Resolution of an AE with residual signs or symptoms
Not Recovered/Resolved (Continuing)	Either incomplete improvement or no improvement of an AE, such that it remains ongoing
Fatal	Outcome of an AE is death. "Fatal" should be used when death is at least possibly related to the AE
Unknown	Outcome of an AE is not known (e.g., a patient lost to follow-up)

### 13.6 Treatment Administered

The Investigator will ensure adequate medical care is provided to patients for any AEs, including clinically significant laboratory values related to study drug. In addition, the Investigator will describe whether any treatment was administered for the AE. "Yes" is used if any treatment was administered in response to an AE and may include treatments such as other medications, hospitalization, surgery, or physical therapy. "No" indicates the absence of any kind of treatment for an AE.

### 13.7 Clinically Significant Assessments

Study assessments including safety laboratory tests, ECGs, and vital signs should be assessed and those deemed a clinically significant worsening from baseline documented as an AE. When possible, a clinical diagnosis for the study assessment should be provided rather than the abnormal test result alone (e.g. urinary tract infection, anemia). In the absence of a diagnosis, the abnormal study assessment itself should be listed as the AE (e.g. bacteria in urine or decreased hemoglobin).

An abnormal study assessment is considered clinically significant if the patient has one or more of the following:

- Concomitant signs or symptoms related to the abnormal study assessment;
- Further diagnostic testing or medical/surgical intervention;
- Discontinuation from study drug treatment.

Repeat testing to determine whether the result is abnormal, in the absence of any of the above criteria, does not necessarily meet clinically significant criteria. The determination of whether the study assessment results are clinically significant must be made by the Investigator. A laboratory abnormality judged to be Grade 4, in itself, may not constitute a SAE unless the clinical status of the patient indicates a life-threatening AE.

### 13.8 Serious Adverse Events

SAEs are generally any AEs that result in one or more of the following:

- Fatal (death, regardless of cause, that occurs during participation in the study or occurs after participation in the study but within 30 days post-study, and is suspected of being a delayed toxicity due to administration of the study drug);
- Is immediately life-threatening (i.e., presents an immediate risk of death at the time of the AE, not an AE that hypothetically might have caused death if it were more severe);
- Requires or prolongs inpatient hospitalization;
- Causes persistent or significant disability/incapacity;
- Is a congenital anomaly/birth defect;
- Other important medical events that may jeopardize the patient and/or require medical or surgical intervention to prevent one of the outcomes listed above.

#### Definition of Inpatient Hospitalization:

An inpatient hospitalization is defined as an admission for any length of time. A hospitalization for administration of study drug, for routine or planned clinical procedures, or for “social” reasons (not the result of any adverse change in the patient’s condition) should not be considered an AE and should not be reported as a SAE. If the patient experiences any adverse change in condition during hospitalization, the condition must be reported as an AE or SAE according to the above definitions.

#### Definition of Life-Threatening Adverse Experience:

An adverse experience is life-threatening if the patient was at immediate risk of death from the event as it occurred (i.e., it does not include a reaction that, had it occurred in a more serious form, might have caused death). For example, drug-induced hepatitis that resolved without evidence of hepatic failure would not be considered life-threatening, even though drug-induced hepatitis can be fatal.

#### Definition of Disabling/Incapacitating Experience:

An adverse experience is incapacitating or disabling if the experience results in a substantial and/or permanent disruption of the patient’s baseline ability to carry out normal life functions.

### 13.9 Serious Adverse Event Reporting

**Any SAE that occurs during this study**, including death from any cause, must be reported by the Investigator (or designee) to the medical monitor **within 24 hours** of awareness of occurrence, regardless of causality or expectedness. The initial notification must contain a description of the observed symptoms and an assessment of causality. Initial reports must be followed up by a written detailed report and submitted within 24 hours of the occurrence of the SAE. The designated contact for SAE reporting is the medical monitor:

PI [REDACTED]  
Neox Clinical Research  
[name], Czech Republic  
Tel: PI [REDACTED]  
Fax: PI [REDACTED]  
Email: PI [REDACTED]

It is imperative that the medical monitor be informed (by email) within 24 hours of a SAE so that SAE reporting to the applicable health authorities can be met within the required time frame. The medical monitor will be responsible for evaluating the reported events for completeness and accuracy and will follow-up with the clinical site for any information missing. The medical monitor or designee will also be responsible for expedited reporting to the applicable health authorities, regulatory agencies and independent ethics committees (IECs)/institutional review boards (IRBs). The medical monitor or designee will be responsible for notifying the Sponsor of SAEs as specified in the safety and communications plans.

Because of the need to report to health authorities all serious adverse reactions in a timely manner, it is vitally important that an Investigator report immediately any adverse experiences which would be considered serious, even if the Investigator does not consider the adverse experience to be clinically significant or drug related. Should the Investigator become aware of a SAE (regardless of relationship to study drug) that occurs within 30 days after the last dose of the study drug, the SAE must be reported in accordance with the procedures specified in this protocol.

All SAEs that are not resolved by the end of the study, or that were not resolved upon discontinuation of the patient's participation in the study, are to be followed until the SAE resolves, the SAE stabilizes, the SAE returns to baseline values (if a baseline value is available), or it is shown that the SAE is not attributable to the study drug or study conduct.

### **13.10 Suspected Unexpected Serious Adverse Reactions (SUSAR)**

SUSARs are SAEs that are possibly related or related to the study drug and are unexpected (i.e., not listed in the Investigator's Brochure). SUSARs will be collected and reported expeditiously, by the Investigator (or designee) to the medical monitor (i.e. within 24 hours of occurrence) who will then report to the competent authorities and independent ethics committees (IECs)/institutional review boards (IRBs) according to regulations, and to the Sponsor as per the safety and communications plans. Medical and scientific judgment of the Investigator is to be exercised in deciding whether expedited reporting is appropriate in other situations, such as for important medical events that are not immediately life-threatening or do not result in death or hospitalization, but jeopardize the patient or the patient population.

### **13.11 Pregnancy**

Females of childbearing potential who have a negative pregnancy test and are enrolled in the study are to continue contraception until 30 days after the last administration of study drug. If the subject becomes pregnant during the study, the study drug should be immediately discontinued, and the Investigator should report the pregnancy to the medical monitor immediately. The Investigator should counsel the subject with regard to the possible untoward effects on the fetus. The subject will be withdrawn from the study and end of study visit performed as soon as possible. The subject should be monitored until the conclusion of the pregnancy. The outcome of all pregnancies must be followed up and documented even if the subject was discontinued from the study.

Pregnancies are considered immediately reportable AEs (**within 24 hours**). All reports of congenital abnormalities/birth defects are SAEs. Spontaneous miscarriages should also be reported and handled as SAEs.

### 13.12 Clinical Laboratory Assessments

Blood and urine samples will be collected according to the Schedule of Activities (Section 2) and analyzed at each individual clinical site. Specific instructions for the collection, processing, and shipment of samples are presented in the Study Laboratory Manual. Laboratory test results that are abnormal and considered clinically significant by the Investigator or designee must be reported as AEs. Screening laboratory results must be available and reviewed by the Investigator before randomization. The safety laboratory test panels are shown in Table 2 below.

**Table 2 - Laboratory Tests Panels**

Serum Chemistry	Hematology	Urinalysis (dipstick)*
Albumin	Hematocrit	Nitrite
Creatinine	Hemoglobin	Urobilinogen
Total protein	Red blood cells	Protein
Potassium	Platelet count	pH
Sodium	Leukocytes	Blood
Calcium	WBC Differential (absolute and %)	Leukocytes
Bicarbonate	Eosinophils	Density
Phosphate	Basophils	Ketones
Alkaline phosphatase	Neutrophils	Bilirubin
ALT	Lymphocytes	Glucose
AST	Monocytes	
Total bilirubin		Other (Urine)
Uric acid		Appearance (clarity and color)
Glucose		
Total cholesterol		
Triglycerides		
Lipase		

\* If dipstick urine is positive for leukocytes, nitrite, urobilinogen, protein, or blood, microscopic examination of urine will be performed for further evaluation.

In addition, according to the Schedule of Activities, the following tests are also performed:

- Pregnancy ( $\beta$ -human chorionic gonadotropin) tests for females of childbearing potential: Serum or urine samples will be obtained as specified in the Schedule of Activities (Section 2) and analyzed at the local labs (serum and urine). The urine pregnancy tests on Day 0 and Day 28 must be negative before dispensing of study drug. A positive result during the study will result in immediate interruption of study drug.

### **13.13 Medical History, Vital Signs and Physical Examinations**

The medical history at screening will include all queries by the medical and clinical staff related to the subject's well-being and history of relevant past medical events/experiences. Medical history will include all demographic data (age, gender, race, body weight adjusted for indoor clothing, height, and BMI) and baseline characteristics. Alcohol and smoking habits will also be recorded. History of intestinal surgical resection or other possible cause of SBS, all recent and current medications and therapies, non-prescription drug intake, and home parenteral nutrition if still administered, will be recorded. Particular attention will be paid to obtaining the history of diarrhea in the 3 months prior to screening, including estimated weekly bowel movement frequency and stool morphology (using the BSFS). This will help in establishing a background diarrhea pattern and confirming patient eligibility for the study.

Vital signs and complete physical examinations will be performed by a medically qualified and licensed individual according to the Schedule of Activities (Section 2).

A complete physical examination (review of all body systems) will be performed at screening and Days 15, 28 and 43 visits.

A complete physical examination includes a review of the following systems: head/neck/thyroid, eyes/ears/nose/throat, respiratory, cardiovascular, lymph nodes, abdomen, skin, musculoskeletal, and neurological. Breast, anorectal, and genital examinations will be performed only when medically indicated. Clinically significant physical examination findings prior to the first dose of study drug will be recorded as medical history; after first dose, any clinically significant abnormal findings in physical examinations should be reported as AEs.

Vital signs include blood pressure (systolic and diastolic), heart rate and body temperature. These will be assessed following a 5-minute rest (seated) and before any scheduled blood sample collection.

### **13.14 Electrocardiograms**

Standard, digital 12-lead ECGs will be performed twice, i.e. during screening and at the End-of Study, Day 43 visit. Sites will use their own ECG equipment.

Performance of all ECGs must adhere to the following guidelines in order to minimize variability and consistent assessments of each patient. ECG recording will be read and interpreted by an internal medicine specialist, at each participating clinical site.

- ECGs will be performed after the patient has been supine for at least 5 minutes;
- The ECG will be performed before any other procedures that may affect heart rate;
- The ECG will be performed during the screening period and on Day 43.

A hard copy of the ECG will be printed and signed by the Investigator at the site.

## **14. STATISTICAL ANALYSIS**

A statistical analysis plan (SAP) will provide details of the methods of analysis to address all study objectives. The SAP may be amended during the course of the study but will be finalized before the database hard-lock for any analysis.

Data summaries by treatment group will be presented. For continuous variables, data will be summarized with the number of patients, mean, standard deviation, median, and minimum and maximum values by treatment group. For categorical variables, data will be tabulated in frequency tables to display the number and proportion of patients for each category by treatment group. Baseline assessments for each outcome variable will be defined as the last measurement obtained before the first dose of study drug.

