-  To be recorded as Prior Medication if taken before the first dose of study drug (i.e. during Screening). Only current medications to be reported (i.e. treatment ongoing at Day -15).
-  From screening to the first dose of the study, AEs will be recorded as screening events or as part of the medical history, as applicable. Any serious adverse events spontaneously reported by subjects up to 30 days following the last day of dosing will be documented.

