**8. SELECTION AND WITHDRAWAL OF PATIENTS**

Subjects who meet all the inclusion criteria and none of the exclusion criteria at the screening visit will be eligible for participation in this study. Continued eligibility will be assessed upon baseline visit at start of Period 1, prior to the first study drug administration.

An effort will be made to include similar proportions of males and females in the study.

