### 9.2.3 Randomization (Visit 2, Day 0)

Eligible SBS patients will be invited to the study site for the selected baseline procedures.

1. Verification of completion of the BM and BSFS screening diary and review of eligibility criteria to decide if patient can continue to be randomized into the study. If yes:
2. Vital signs will be measured (heart rate, blood pressure and body temperature).
3. A urine pregnancy test will be performed if applicable. This test must be negative to dispense study medication.
4. Randomized patients will receive a 14-day supply of study treatment. Patients will be instructed to start taking their study medication the next day in the morning, i.e. on Day 1, and for 14 consecutive days, until Day 14 inclusive.
5. Patients will be given a new BM and BSFS diary for Period 1, in which they will need to record daily the number of stools and their form, using the BSFS, for Days 1 to 14 inclusive. Proper instructions will be provided for the use of the BSFS. They will also be provided the BM/BSFS diary for the Washout period, to be completed during Days 15 to 28.
6. Patients will be given a VAS questionnaire to complete on site. The four 11-point VAS scales (from 0 to 10), will be used by the patients to make an overall assessment of diarrhea, abdominal pain, bloating and urgency experienced during the last 24 hours. Zero will mean no symptom at all, and 10: very severe. The VAS assessments will be made at Days 0, 15, 28 and 43, but not during screening.

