#### **9.2.7 Washout (Visit 4, Day 28)**

On the last day of the Washout period (**Day 28**), patients will return to the clinical with their BM/BSFS diary. Patients will arrive in the fasted state (i.e. fast for 4 hours before visit). The following assessments and procedures will be performed:

1. Complete physical examination;
2. Measurement of vital signs including heart rate, blood pressure and body temperature;
3. Measurement of body weight, and calculation of BMI;
4. All safety laboratory tests, including at a minimum: urinalysis (dipstick), hematology, serum chemistry;
5. A urine pregnancy test will be performed if applicable. This test must be negative to dispense study medication for Period 2.
6. Recording of concomitant medications;
7. Verification of the BM and BSFS Washout diary. The Washout diary will be given back to the patient and they will be instructed to continue using the diary for Day 28. The patient will also be provided a new diary for Period 2.
8. The VAS symptoms questionnaire will be completed by the patient on site.
9. Recording of AEs;
10. Study medication for Period 2 will be supplied at the end of the visit, with instructions to begin dosing on Day 29.

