### 14.7.2 Clinical Laboratory Assessments

Safety laboratory variables (e.g., hematology, biochemistry, and urinalysis results) will be presented in the International System of units at each time point using descriptive statistics (mean, standard deviation, median, minimum, and maximum). Change from baseline values for each variable will also be presented by treatment group. The number and percentage of patients with shift changes from baseline (normal, high, and low according to the reference range as provided by the laboratories) to post-baseline will be tabulated by treatment group.

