### 14.7.3 Vital Signs

Vital signs (blood pressure, temperature and heart rate) will be presented at each time point using descriptive statistics (mean, standard deviation, median, minimum, and maximum). Change from baseline values for each variable will also be presented by treatment group.

The number and percentage of patients with shift changes from baseline to post-baseline based on abnormal criteria will be presented by treatment group.

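### By-dose laboratory and vital-sign shift tables use one pre-Day 1 baseline for both crossover periods, so an abnormality from Period 1 or the washout that is still present on Day 43 counts as a new shift under the Period 2 dose

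*Combined protocol and SAP*

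**What the plan says.** The baseline rule is in section 14 (Statistical Analysis) and covers all variables: "Baseline assessments for each outcome variable will be defined as the last measurement obtained before the first dose of study drug".

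The safety sections apply it by dose. Section 14.7.2 has laboratory shifts from baseline "to post-baseline will be tabulated by treatment group". Section 14.7.3 says: "The number and percentage of patients with shift changes from baseline to post-baseline based on abnormal criteria will be presented by treatment group". Neither section defines another baseline. Section 14.2 has safety analysed by the treatment actually received, and sections 7.2.1 and 7.3 have all 18 patients receiving both doses.

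Other text reads the start of dosing as a single event. Section 8 says: "Continued eligibility will be assessed upon baseline visit at start of Period 1, prior to the first study drug administration". Sections 14.3 and 14.7.1 use the first dose of study drug as one trial-wide landmark for prior medication and for pretreatment adverse events.

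The Schedule of Activities (section 2) has laboratory tests on Days -15, 15, 28 and 43, and vital signs on those days and on Day 0. Period 2 dosing starts on Day 29. The Day 28 visit (section 9.2.7) therefore gives pre-dose values for Period 2, including "All safety laboratory tests, including at a minimum: urinalysis (dipstick), hematology, serum chemistry". No text makes these the Period 2 reference, and no text says which dose the Day 28 visit belongs to in the shift tables.

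**The concern.** A shift table by dose is read as the number of patients whose value moved out of range on that dose. Half of each dose column (9 of 18 patients, by the sequence sizes in Table 1) comes from Period 2. For those patients the reference value was taken before a full course of the other dose and a 14-day washout. Whatever went out of range in that time and has not recovered by Day 43 is booked as new under the second dose, even if it was already abnormal on Day 28, before that dose began.

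Safety and tolerability are secondary objectives (section 6.2) in a trial meant to select a dose (section 6.1), so these tables should show what happened on the dose named at the head of the column. With 18 patients, one or two misplaced cases are visible in a percentage.

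**Working it through.** The plan gives no figure on this point to reproduce, so the check is a count by case.

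**Inputs.** The baseline rule is from section 14 and the visit days from section 2. Day 15 is taken to belong to the Period 1 dose and Day 43 to the Period 2 dose, which follows from analysis by treatment received (section 14.2). There are 18 patients per dose column. Persistence is not given anywhere and is left open.

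**Step 1: four patient patterns.** N is normal and H is out of range. The pre-Day 1 value is from Day -15 for laboratory tests and Day 0 for vital signs.

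| Pattern | Pre-Day 1 | Day 15 | Day 28 | Day 43 | Plan's baseline: Period 1 dose / Period 2 dose | Period-specific baseline: Period 1 dose / Period 2 dose |
|---|---|---|---|---|---|---|
| a. Arises in Period 1, persists | N | H | H | H | N to H / **N to H** | N to H / H to H |
| b. Arises in washout, persists | N | N | H | H | N to N / **N to H** | N to N / H to H |
| c. Arises in Period 1, recovers | N | H | N | N | N to H / N to N | N to H / N to N |
| d. Recovers, recurs in Period 2 | N | H | N | H | N to H / N to H | N to H / N to H |

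The result is the same for either sequence. The two baselines differ only in patterns a and b. Under the plan's rule, pattern a is a new shift under both doses. Pattern b is a new shift under a dose that had not been started when the abnormality appeared.

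**Step 2: size per case.** Each pattern a or b patient adds one to the Period 2 dose's numerator: 1/18 = 5.6 points, 2/18 = 11.1 points, 3/18 = 16.7 points. With only the 15 patients that Table 3 requires for a 25% difference, one case would be 1/15 = 6.7 points. This supposes that the patient would not have shifted on the second dose anyway.

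**Step 3: effect on the contrast between doses (all counts assumed).** Let the true shifts be High 4/18 and Low 2/18, split evenly over sequences, so the true gap is 2/18 = 11.1 points. Let kH be the High-first cases and kL the Low-first cases that persist to Day 43. The displayed gap is (2 + kL - kH)/18.

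| kH | kL | Displayed gap |
|---|---|---|
| 0 | 0 | 2/18 = 11.1 points |
| 1 | 1 | 2/18 = 11.1 points |
| 1 | 0 | 1/18 = 5.6 points |
| 2 | 0 | 0/18 = 0.0 points |
| 0 | 1 | 3/18 = 16.7 points |

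The direction is not fixed.

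**Step 4: mean change.** For a patient with both visits and one common baseline B, the between-period difference is (Day 43 - B) - (Day 15 - B) = Day 43 - Day 15. B cancels, so the between-dose contrast in mean change does not depend on which common baseline is used.

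**Step 5: what a Day 28 baseline would do to mean change.** Let H and L be the true mean changes, with 50% of each dose's effect left on Day 28 and 25% on Day 43 (assumed).

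- Pre-Day 1 baseline: gap = (H - L) - 0.25(H - L)/2 = 0.875(H - L), understated by 12.5%.
- Day 28 baseline: gap = (H - L) + (0.50 - 0.25)(H - L)/2 = 1.125(H - L), overstated by 12.5%.

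For means, moving the baseline replaces one distortion with another.

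**The case against.** The strongest reply has four parts.

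First, section 14 leaves the detail to a SAP that may be amended until database hard-lock, and assigning visits to doses is ordinary SAP content. That stands as a limit: the point concerns the rule as written, and a SAP could override it. A SAP that simply follows it would carry the problem over. Section 12.1 does speak of a first baseline, but for the bowel-movement diary only, and no second one is defined there or for the safety variables.

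Second, the 14-day washout is there to prevent carry-over (section 5.7). If it works for every variable, pattern a does not arise from drug effect. But section 5.7 supports the length by precedent in earlier trials and gives no evidence on laboratory recovery. Pattern b needs no carry-over at all, only an intercurrent abnormality that starts in the washout.

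Third, little is left exposed. Section 14.7 has no statistical comparisons and lists all safety data, Day 28 is summarised at its own time point, and section 13.7 has "those deemed a clinically significant worsening from baseline documented as an AE". This stands, and it is why the point is minor. What remains is shifts that fall short of an adverse event.

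Fourth, a Day 28 baseline has its own fault. A patient already abnormal on Day 28 cannot show a new shift in Period 2, even if the second dose is what sustains the abnormality. In the step 3 illustration, one High-first patient of this kind whom Low would also have shifted takes the Low column from 2/18 = 11.1% to 1/18 = 5.6%. This also stands, and it is why the fix keeps both displays.

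A reader might infer that the mean-change tables are wrong in the same way, because a Period 2 change also spans dosing days on the other dose. The documents do not support that. The common baseline cancels from the between-dose contrast (step 4), so any distortion there is carry-over, which would affect the raw values just as much.

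**Conclusion.** The point holds for the by-dose laboratory and vital-sign shift tables only, and it is minor. As written, the rule counts an abnormality that began in Period 1 or the washout and is still present on Day 43 as a new shift under the Period 2 dose, and a persisting Period 1 abnormality under both doses. Each case is worth 1/18 = 5.6 points on that dose's shift rate. If no case persists to Day 43, the effect is zero.

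This rests on reading the first dose of study drug as the Day 1 dose, on Day 43 being tabulated under the Period 2 dose, and on no SAP text replacing the rule. How many cases would persist, and whether the gap between doses would shrink or widen, cannot be said from the documents; the gaps in step 3 are illustrations.

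A reader might also infer that dose selection is compromised. It is not: the primary endpoint is bowel-movement frequency (section 7.1.1), and no decision rule in the protocol uses these tables. ECG is outside the point, because it is recorded only at screening and on Day 43 and section 14.7.4 does not split it by dose.

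**What to change.** For the by-dose shift tables in sections 14.7.2 and 14.7.3, define baseline as the last value before the first dose of each period: Day -15 (laboratory) or Day 0 (vital signs) for Period 1, and Day 28 for Period 2. State that Day 15 belongs to the Period 1 dose, Day 43 to the Period 2 dose, and that Day 28 is the Period 2 pre-dose value.

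Keep the shift from the pre-Day 1 baseline as a companion display, so that an abnormality sustained by the second dose is not hidden. Leave the mean-change tables on the pre-Day 1 baseline.

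The cost is a few sentences and one further set of descriptive shift tables for vital signs and the laboratory panels in Table 2 (17 chemistry analytes, haematology and urinalysis). It needs no new data and no statistical test.
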